7.3 Withdrawal and Early Discontinuation Criteria and Procedures

When the study is terminated for a given patient, the nature of termination will be documented (scheduled end or early termination/discontinuation). In the event of premature termination/discontinuation, justification will be provided and the name of the decision maker for the discontinuation will be documented.

If the study as a whole is prematurely terminated or suspended, the Independent Ethics Committees (IEC) and the appropriate regulatory authorities will be promptly informed and provided with the reasons for termination or suspension by the Sponsor.

7.3.1 Discontinuation Criteria Related to the Study

Criteria for discontinuation / termination of the entire clinical study include (non-exhaustive list):

- Unexpected high frequency of adverse (device) reactions / adverse (device) effects during the study which does not justify a continuation of the study
- Patients cannot be recruited in sufficient numbers

7.3.2 Discontinuation Criteria Related to the Study Site

Discontinuation of the clinical study in an individual study site may occur because of various reasons including but not limited to:

- Failure of the Investigator to comply with the EN ISO 14155:2011, ICH GCP E6 (rev2), and/or applicable regulatory requirements;
- Submission of knowingly false or incomplete information from the site to Philips, the Study Monitor or authorities;
- Repeated non-compliance with protocol requirements including insufficient data quality (missing data in Case Report Forms (CRFs) occurring repeatedly);
- Failure of the Investigator at a site to enroll patients into the study at an acceptable rate;
- Personnel change without appropriate information to the Sponsor.

7.3.3 Discontinuation Criteria related to the Patient

Patients will be advised in the informed consent forms that they have the right to withdraw from the study at any time without prejudice, and may be withdrawn at the Investigator's / Sponsor's discretion at any time, when the withdrawal is considered to be in the interest of the patient. In the event of a patient dropping out of the study or withdrawing from the study, the withdrawal/study termination page in the CRF has to be completed. On the withdrawal page of the CRF the Investigator should record the date of the withdrawal, the person who initiated withdrawal and the reason for withdrawal.

The following are reasons for patient dropout/withdrawal:

- i) Withdrawn by the Investigator due to:
 - Adverse Event, Serious Adverse Event
 - Protocol deviation (e.g. administration of an excluded treatment, failure to comply with scheduled visits, ...)
 - Pregnancy
- ii) At the patient's request due to:
 - An Adverse Event / Device Effect for which the Investigator did not consider removal necessary;
 - Withdrawal of consent.

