11.2 Level of significance

The level of significance for all comparisons is set at 0.05 using two-tailed tests.

Confidence level is set at 0.95 (two-sided) for all primary and secondary endpoints.

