11.3 Patient selection for analyses

There will be three analysis populations defined for the study:

- The Safety population (SAF) will include all patients who signed an informed consent form.
Safety analyses will be performed on the SAF population.
- The Full Analysis Set (FAS) population will include all patients who signed an informed consent form and performed the study procedures, whatever their assigned treatment group by randomization.

Description of demographic and baseline characteristics as well as analyses of primary and secondary endpoints (other than safety endpoints) will be performed on the FAS population.

- The per protocol (PP) population will include patients from the FAS population without major protocol deviation that might significantly affect the completeness, accuracy, and/or reliability of the study data. Deviations involving possible bias regarding the primary endpoint analysis will be considered as major deviations. Protocol deviations will be further defined in the statistical analysis plan.

The PP population will be used for the supportive analyses of the primary and main secondary endpoints (other than safety endpoints).

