11.8 Sample Size

The sample size calculation is based on a preliminary study evaluating the primary criteria (macro-relief scoring changes between D0 and D90 after manual compared to electric brushings). In this preliminary study, we have measured a threshold value of $\Delta E = 0.67$ on the primary criteria between manual brushing and electric brushing, associated with a standard deviation of 0.84. Using a

bilateral two-group test with a 0.05 two-sided significance level and a power (1- β) of 0.80 yielded a sample size of 25 subjects per group (34 subjects when considering a power (1- β) of 0.90).

We can add 20% for potential dropouts. Thus, 30 subjects per group is evaluated, i.e. 60 subjects are required in total.

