13.2 Organization and evaluation

The study period during which (serious) adverse events will be recorded/reported is defined as the period from patient inclusion to the end of study participation.

The clinical course of each (serious) adverse event will be followed up until the event (or its sequelae) resolves or stabilizes at a level acceptable to both the Investigator and Sponsor,

Every effort will be made by the Investigator to explain each AE and assess its causal relationship to the Investigational Product. The Investigator will use the following definitions and categories to assess adverse events:

Seriousness:

- No: no fulfilment of Serious AE criterion
- Yes: fulfilment of SAE criterion (see section 13)

Severity/Intensity:

- Mild: Transient or mild discomfort, no modification of procedure or medical intervention required
- Moderate: Discomfort causes interference with usual activities, no or minimal modification of procedure or medical intervention required
- Severe: Inability to work or to do usual activity, medical intervention indispensable

There is a distinction between the terms “severe” and “serious” for an AE. Severe is a measurement of intensity; thus, a severe reaction is not necessarily a SAE. For example, a headache may be severe in intensity, but would not be serious unless it met one of the criteria for SAEs listed in section 13.1.3.

Action undertaken in regard to the Investigational Product:

- None
- Investigational Product postponed
- Investigational Product discontinued

AE therapy:

- Yes: remedial treatment necessary
- No: remedial treatment unnecessary

Final outcome:

- Recovered without sequelae
- Recovered with sequelae
- Ongoing
- Unknown
- Death
- Improving/worsening

Causality (relationship with the Investigational Product):

- Certain: temporal correlation plausible, other causes excluded
- Probable: temporal correlation reasonable, other causes unlikely
- Possible: temporal correlation reasonable, other causes possible, not assessable
- Unlikely: No temporal correlation, other causes probable, not assessable
- Not related: definitely no causal relationship (see section 10.1.8)

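### Section 7.3.3 allows withdrawal from the study for an adverse event or deviation without keeping the Day 90 assessment, so the abrasion change used for sizing can be lost, plausibly informatively

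*Protocol*

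**What the plan says.** Section 7.3.3 says that a patient may be withdrawn at the discretion of the investigator or sponsor "when the withdrawal is considered to be in the interest of the patient". It then lists reasons for withdrawal by the investigator: an adverse event or serious adverse event, pregnancy, and "Protocol deviation (e.g. administration of an excluded treatment, failure to comply with scheduled visits". When a patient leaves, a withdrawal page is completed, on which "the Investigator should record the date of the withdrawal, the person who initiated withdrawal and the reason for withdrawal". The section asks for no photograph or clinical measure.

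Other sections bear on what happens next:

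- Sections 9.1 and 9.3 schedule one visit after baseline, at Day 90, and no early-termination assessment.
- Section 13.2 follows an adverse event until it resolves or stabilises and has "Investigational Product discontinued" among the actions that can be recorded for it. It does not mention the abrasion score.
- Section 11.1 states that missing values are not replaced.
- Section 11.3 runs the primary analysis on the FAS. The PP set "will include patients from the FAS population without major protocol deviation that might significantly affect the completeness, accuracy, and/or reliability of the study data".
- Section 8.6 prohibits no concomitant therapy.
- Section 11.8 sizes the trial on the change in macro-relief score from D0 to D90.

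**The concern.** Stopping a product and leaving a study are different events, and Section 7.3.3 treats them as one. A patient taken off the brush because of an adverse event can be recorded as withdrawn, with nothing that asks for the Day 90 photographs. With one post-baseline visit and no replacement of missing values, that patient contributes no D0 to D90 change.

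The loss is unlikely to be random. The primary score adds up erythema, inflammation, bleeding, recession and erosion (Section 11.5). A gingival adverse event is likely to involve one or more of these, so the patients whose scores go missing may be those who would have scored worst. In a superiority trial about gingival harm, the arm that loses such patients looks better than it is. The comparison could be biased in either direction, depending on which arm that is. No later analysis can recover photographs that were not taken.

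**Working it through.** **1. The planning figure.** Inputs from Sections 11.2 and 11.8: two-sided 5% level, difference 0.67, SD 0.84, power 80% or 90%.

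n per group = 2 × (z for alpha + z for power)² × (SD / difference)²

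- 80%: 2 × (1.960 + 0.842)² × (0.84 / 0.67)² = 24.7, rounded up to 25
- 90%: 2 × (1.960 + 1.282)² × (0.84 / 0.67)² = 33.0, rounded up to 34

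Both stated figures reproduce. The planned 30 per group is 25 × 1.20.

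**2. What the dropout allowance covers.** Power by the same normal approximation, by number of Day 90 scores per group:

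| Scores per group | Power |
|---|---|
| 30 | 0.871 |
| 27 | 0.834 |
| 25 | 0.805 |
| 24 | 0.789 |
| 20 | 0.713 |

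If 20% of the 30 are lost, 24 remain and power is 0.789, just under the target. The allowance therefore nearly covers the loss of numbers. It does nothing about bias.

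**3. Size of a bias from informative loss.** Let a share d of one arm be withdrawn, and let their mean Day 90 score be k points higher (worse) than that of the patients retained, whose mean is m.

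Full-arm mean = (1 − d) × m + d × (m + k) = m + d × k

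The retained patients thus understate the arm's mean by d × k. The protocol gives neither d nor k. The values below are assumptions: d from 5% to 20%, and k of 1 or 2 times the planning SD of 0.84.

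| d | k = 0.84 | Share of 0.67 | k = 1.68 | Share of 0.67 |
|---|---|---|---|---|
| 5% | 0.04 | 6% | 0.08 | 13% |
| 10% | 0.08 | 13% | 0.17 | 25% |
| 20% | 0.17 | 25% | 0.34 | 50% |

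The bias in the between-arm difference is d × k in one arm minus d × k in the other. It is zero when withdrawals are equal and alike in both arms.

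**4. Passages that do not fit together.** Section 11.3 forms the PP set by taking major deviators out of the FAS, so the FAS is meant to hold deviators. Section 7.3.3 lists a deviation as a reason to leave the study. Section 7.3.3 also gives use of an excluded treatment as an example, while Section 8.6 excludes none.

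**The case against.** The strongest reply is that Section 7.3.3 does little harm in practice. Much of that reply stands.

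- A reader might infer that patients with an event or deviation must be removed. The text says they may be withdrawn and then lists reasons. Removal is permitted, not ordered.
- A reader might infer that nothing more is collected, not even the brush. Sections 8.4 and 8.5 provide for accounting and retrieval of used product, and Section 13.2 continues follow-up of the event. What is missing is a request for the abrasion score. The section is silent on exit photographs; it does not forbid them.
- A reader might infer that deviators vanish before Day 90, so that the FAS with Day 90 data is almost the PP set and the PP analysis loses its use. The documents do not support this. No visit is planned between baseline and Day 90, and brush use, brush wear and toothpaste weight are assessed at Day 90 or later. A non-adherent patient found then can still have a score, stay in the FAS and be left out of PP. Missing the only follow-up visit means that the score is already absent. A late attender is a possible exception, since Section 14.1.2 refers to a visit window that Section 9.3 does not give.
- A reader might take it as settled that withdrawn patients belong to the FAS. Section 11.3 requires that the study procedures were performed and does not say which. If all are meant, the FAS is a set of completers. The Day 90 score is lost on either reading.
- Section 4.3 expects very few adverse effects, so the lower end of the assumed range may be the more realistic one.
- The immediate post-brushing score on Day 1 would normally already exist.

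None of this supplies the missing instruction. The adverse-event route remains open, and it is the one most closely tied to the endpoint.

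**Conclusion.** The point holds as a gap in a conduct rule. As written, the protocol permits withdrawal from the study for an adverse event, deviation or pregnancy and nowhere keeps the Day 90 assessment for such patients. The D0 to D90 change can be lost in patients whose events overlap with the score.

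The size is unknown. Under one-arm withdrawal of 5% to 20% and a gap of 1 to 2 SD, the bias is about 0.04 to 0.34 points, 6% to 50% of the planning difference. The upper end needs the whole 20% allowance to be informative loss in one arm and no such loss in the other. The conclusion does not rest on the FAS definition or on any claim about the PP analysis. It is worth correcting because the change is cheap and must be made before the data are lost.

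**What to change.** In Section 7.3.3, distinguish a patient who *stopped using the assigned brush* from one who *withdrew consent to follow-up*. State that every randomised patient who has not withdrawn consent is still invited to the planned Day 90 visit for photographs and clinical measures, with the brush then in use recorded.

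Reconcile two pairs of passages: protocol deviation as a withdrawal reason in Section 7.3.3 with Section 11.3, where major deviation leads only to exclusion from PP; and the excluded-treatment example in Section 7.3.3 with Section 8.6. When a brush should be stopped remains a clinical decision, on which no view is given here.

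The cost is protocol wording and an eCRF entry for the brush in use and the date the assigned one was stopped; the visit is already planned. The downside is that some Day 90 scores will come from patients no longer using the assigned brush, which may dilute the contrast slightly.

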8 INVESTIGATIONAL PRODUCT

All specified devices and products to be used in the study will be provided by Philips Sonicare.

8.1 Name and Description of the Investigational Product

In this study both products, Philips Sonicare ProtectiveClean® and the manual toothbrush (Pierre Fabre Inava® 20/100) will be used within the indications. The test sites will be treated with the investigational device following the instructions of this protocol.

Investigational devices will be made available to the investigation site by the Sponsor. If any defect in the Investigational Product is observed, the study manager or monitor will be informed. A sodium monofluorophosphate (1450 ppm F) toothpaste (elmex® SENSITIVE PROFESSIONAL) will be provided to the patient.

8.1.1 *Indications for use*

The indication studied is using of an electric toothbrush Philips Sonicare ProtectiveClean® HX6848/92 associated with a C2 Optimal Plaque Defense head HX9022/10, in routine oral hygiene and to assess the possible effects on hard and soft tissue.

8.1.2 *Duration of treatment*

The overall duration of the study for the patient will be 90 days from the time of the baseline.

8.1.3 *Packaging and Labelling*

The boxes will be labelled in accordance with ISO 14155:2011 (Paragraph 5.10). Labels will indicate that the device is exclusively intended for use in the study and will identify the study number, Sponsor and patient code.

8.2 Storage

The Investigational Products will be supplied to the pharmacist or any other designated person. Investigational products can be stored at room temperature in a dry area. Non-adherence with the storage conditions could alter the performance of the Investigational Product.

8.3 Instructions for Use

The instructions for use of Philips Sonicare ProtectiveClean® and Pierre Fabre Inava® are provided in the products notices (see appendices in sections 19.2 and 19.3). The investigators will give the patients the following oral hygiene instructions:

Place the bristles against the teeth at a 45° angle, towards the gum line and start brushing. Depending on the allocation group the following instructions will be given:

Electric toothbrush: Apply light pressure and move the brush head slowly horizontally without scrubbing across the teeth to brush all dental surfaces in a regular movement. It is not necessary to do any other movement. The ProtectiveClean Sonicare® brush will generate small vibrations every 30 seconds so the patient can adjust the pace of his movement to the global brushing time of 2 minutes.

Manual toothbrush: The “rolling” modified Bass technique should be used: the head of the brush must be rotated upwards on the lower teeth and downwards on the upper teeth towards the occlusal surface. The occlusal surfaces are cleaned using the scrub technique (the toothbrush is swept along the teeth backwards and forwards). In palatal/lingual sites a slight horizontal movement can be combined with a vertical translation as described above.

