4 INTRODUCTION

4.1 Background and rationale

Gingival recession is defined as the apical shift of the gingival margin with respect to the cemento-enamel junction it is associated with attachment loss and with exposure of the root surface to the oral environment (Cortellini and Bissada, 2018). The etiology of gingival recessions remains unclear. Among predisposing factors tooth brushing has been suggested. A few systematic reviews support or refute the association between tooth brushing and gingival recession. In one systematic review, among the 18 examined studies, one concluded that the toothbrushes significantly reduced recessions on facial tooth surfaces over 18 months, two concluded that there appeared to be no relationship between tooth brushing frequency and gingival recession, while eight studies reported a positive association between tooth brushing frequency and recession. Several studies reported potential risk factors like duration of tooth brushing, brushing force, frequency of changing the tooth-brushing technique (Cortellini and Bissada, 2018).

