Philips Sonicare brush heads work with sonic technology: High-speed vibrations in the toothbrush handle power up to 62,000 brush movements per minute that whip up the toothpaste into gentle cleaning bubbles, driving them deep between the teeth and the gum for additional cleaning. The sonic toothbrush Philips Sonicare ProtectiveClean has an intuitive pressure sensor that helps patients to guide their brushing technique. One of the advantages of using this toothbrush is that pressure sensor provides real-time feedback so patient will adopt a softer touch to protect teeth and gums. This toothbrush works on 2 modes to remove plaque gently and effectively. On some Philips Sonicare sonic brushes, a program named "Gum Care" also adds an extra minute of reduced-power brushing to gently massage the gums, improving gum health. In addition, the BrushSync feature tracks brush head effectiveness based on brushing time and pressure and alerts patients when it is time for replacement.

The toothbrush head Philips Sonicare Optimal Plaque Defense possesses densely-packed, high-quality bristles that remove up to 7x more plaque than a manual toothbrush (Philips Oral Healthcare, unpublished data). This brush head works with a sonic technology, high-speed vibrations in the toothbrush handle power up to 62,000 brush movements per minute that whip up the toothpaste into gentle cleaning bubbles, driving them deep between the teeth and the gum for cleaning. Philips Sonicare ProtectiveClean has an intuitive pressure sensor that helps patients to guide their brushing technique. This pressure sensor provides a real-time feedback, thus encouraging the subject to adopt a softer touch in order to protect his/her teeth and gums. This feature is one of the benefits of using this toothbrush. This toothbrush works on 2 modes to remove plaque gently and effectively. The Gum Care mode also adds an extra minute of reduced -power brushing to gently massage the gums, improving gum health

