Usually patients brush their teeth with a toothpaste. To minimize the bias of using abrasive toothpaste the choice of a sodium monofluorophosphate (1450 ppm F) toothpaste (elmex® SENSITIVE PROFESSIONAL) with a low degree of abrasion as defined by the relative dentine abrasion (RDA) was made. RDA –is an index of tooth abrasion by toothpaste. The RDA scale ranges from 0 to 250. The 0-70 range is considered as low abrasion, i.e. safe for cement, dentine and enamel (González-Cabezas et al., 2013). According to this standard, toothpastes with an RDA value below 250 can be used safely for a lifetime. However, the RDA value is only one of the factors that cause tooth wear during brushing. An *in vitro* study concludes that, regardless of the properties of the toothpastes (desensitizing and/or anti-erosive) the lower surface abrasion is associated with higher concentration of Ca^{2+} and PO_4^{3-} , presence of Sn^{2+} , higher percentage weight of solid particles, smaller particle size, and lower wettability (João-Souza et al., 2017).

Therefore, the aim of this study is to compare the gingival abrasion of a sonic toothbrush (Sonicare ProtectiveClean® Optimal Plaque Defense head) as test group with a conventional manual toothbrush (control group) in regular patients attending the Service of Odontology of the Hôpital Rothschild (AP-HP).

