- Press the power button once to turn on the toothbrush.
- Press a second time **within 2 seconds** to change the intensity.
- Press a third time **within 2 seconds** to pause.

After 2 seconds of brushing, pressing the power button again will also pause the toothbrush.

Using your Philips Sonicare

Brushing instructions

1 Press the brush head onto the handle in such a way that the bristles will face the front of the handle. (Fig. 3)

2 Firmly press the brush head down onto the metal shaft until it stops.

Note: it is normal to see a slight gap between the brush head and the handle.

3 Wet the bristles. (Fig. 4)

4 Apply a small amount of toothpaste on the bristles. (Fig. 5)

5 Place the toothbrush bristles against the teeth at a slight angle (45 degrees), pressing firmly to make the bristles reach the gumline or slightly beneath the gumline. (Fig. 6) A change in vibration (and a slight change in sound) alerts you when you apply too much pressure while brushing.

Note: Keep the center of the brush in contact with the teeth at all times.

6 Press the power on/off button to turn on the Philips Sonicare. (Fig. 7)

7 Gently keep the bristles placed on the teeth and in the gumline. Brush your teeth with small back and forth motion so the bristles reach between the teeth. (Fig. 8)

Note: The bristles should slightly flare. Do not scrub.

8 To clean the inside surfaces of the front teeth, tilt the brush handle semi-upright and make several vertical overlapping brushing strokes on each tooth. (Fig. 9)

9 To make sure you brush evenly throughout the mouth, divide the mouth into 4 sections using the Quadpacer feature. (Fig. 10) The quadpacer feature beeps after 30 seconds.

10 Brush for the full 2 minutes following the Quadpacer. (Fig. 11) After 2 minutes, the toothbrush will automatically shut off.

–After you have completed the brushing cycle, you can spend additional time brushing the chewing surfaces of your teeth and areas where staining occurs. (Fig. 12)

Your Philips Sonicare toothbrush is safe to use on;

–Braces (brush heads wear out sooner when used on braces)

–Dental restorations (fillings, crowns, veneers)

Note: When the Philips Sonicare toothbrush is used in clinical studies, it must be used in the Clean mode (for plaque and gum health claims) with EasyStart turned off.

Features

–EasyStart

–Brush head replacement reminder

–Pressure sensor

–Quadpacer

EasyStart

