19.3 Appendix 3: Pierre Fabre Inava 20/100® Instructions for use

Inava 20/100® Pierre Fabre Oral Care France manual toothbrush

Manual toothbrush with bristles with rounded end (diameter: 20/100ème in Tynex®) and soft /ergonomic handle (ACL: 3401561130767).

The INAVA system consists of an INAVA 20 / 100th (ACL: 3401599691391) toothbrush mounted on a lightweight and ergonomic foam handle to facilitate grip of the brush. Indeed, for some people, brushing can become a real journey of the combatant, especially when the hands are painful or lose in dexterity; then simple manipulation can become difficult.

Instructions for use can be found in the following website:

<https://fr-fr.pierrefabre-oralcare.com/inava/inava-souple-20100-brosse-dents>

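### Section 8.3 scripts light pressure for the sonic-brush arm only, although the primary endpoint is gingival abrasion; the sonic brush's intensity setting is also neither fixed nor recorded.

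*Protocol*

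**What the plan says.** Protocol section 8.3 sets out what the investigators tell patients. Both arms get the same sentence on placing the bristles at 45°. The text then splits by allocation.

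- **Sonic brush:** "Apply light pressure and move the brush head slowly horizontally without scrubbing across the teeth".
- **Manual brush:** a rolling modified Bass technique, in which "the head of the brush must be rotated upwards on the lower teeth and downwards on the upper teeth towards the occlusal surface", with scrubbing reserved for the occlusal surfaces. No pressure level is stated.

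Section 4.1 gives the aim in terms of the brush: "the aim of this study is to compare the gingival abrasion of a sonic toothbrush", against a conventional manual brush. The same section lists "potential risk factors like duration of tooth brushing, brushing force" when discussing recession. It also describes the sonic brush's pressure sensor as "thus encouraging the subject to adopt a softer touch in order to protect his/her teeth and gums". Section 11.5 shows recession as one of the five items in the primary score.

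Section 6.3 lists oral hygiene instructions, manufacturer's instructions and professional recommendations for both arms. For the manual brush, Appendix 3 reproduces no brushing text: "Instructions for use can be found in the following website".

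For the sonic brush, Appendix 2 lets the user choose low or high intensity, with low as the default at first use. Its note on clinical studies fixes Clean mode and EasyStart off. It does not fix intensity. It also lets the user switch the pressure sensor off.

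**The concern.** The trial is meant to show whether one brush abrades the gingiva less than the other. Other influences on abrasion are held equal on purpose: section 4.1 chooses a low-abrasion toothpaste to limit bias, and section 6.6 sets the same brushing time in both arms. Pressure, which section 4.1 also treats as relevant to the gums, is coached in writing for one arm only.

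Randomization and examiner blinding do not remove a difference in instruction that the protocol itself prescribes. If light-pressure coaching lowers the abrasion score, the direction favours the test arm, and a significant result could be credited to the brush when part of it belongs to the coaching. The sensor's feedback is part of the device. The investigator's spoken sentence is not.

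The intensity gap is of a different kind. It does not make the arms unequal in any way that has been shown, but it leaves the report unable to say at which power setting the abrasion result was obtained.

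**Working it through.** **1. The two scripts side by side (section 8.3).**

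| Element | Sonic brush | Manual brush |
|---|---|---|
| Bristle angle | 45° (shared) | 45° (shared) |
| Movement | slow, horizontal | rolling modified Bass |
| Scrubbing | told not to | occlusal surfaces only |
| Pressure | light | not stated |

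Movement has to differ between the two brushes. Pressure does not: light pressure can be asked of either.

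**2. Where else pressure advice could reach control patients.** Section 6.3 gives both arms manufacturer's instructions and professional recommendations. The manual brush's instructions are on a website. The only professional advice written out is that in 8.3. So the documents show that 8.3 is silent on pressure for controls. They do not show that controls hear nothing about it.

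**3. Where intensity or pressure could be recorded.** The flow chart (9.1), the visit procedures (9.3) and the compliance section (9.4) collect patient-reported usage, weeks of use, brush wear on a 0 to 4 scale, and toothpaste weight. None names intensity. Brush wear reflects force and brushing time together, so it cannot stand in for either pressure or intensity.

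**4. The plan's own sample size (section 11.8).** Inputs: difference 0.67, SD 0.84, two-sided alpha 0.05.

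n per group = 2 × (z for alpha + z for power)² × SD² / difference²

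- 80% power: 2 × (1.960 + 0.842)² × 0.84² / 0.67² = 24.7, so 25.
- 90% power: 2 × (1.960 + 1.282)² × 0.84² / 0.67² = 33.0 (33.03 before rounding), so 34.

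Both stated figures reproduce. The planned 30 per group is 25 × 1.2.

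**5. How small a difference is significant.** Smallest significant observed difference = t(0.975, 2n − 2) × 0.84 × √(2/n).

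- n = 25: 2.0106 × 0.2376 = 0.478 points.
- n = 30: 2.0017 × 0.2169 = 0.434 points.

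**6. Sensitivity, for illustration only.** Assume that the brushes do not differ and that the instruction alone shifts the mean score by d. The chance of a significant two-sided t-test (noncentral t, SD 0.84) is then:

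| Assumed d (share of 0.67) | 25 per group | 30 per group |
|---|---|---|
| 0.067 (10%) | 5.9% | 6.1% |
| 0.1675 (25%) | 10.6% | 11.8% |
| 0.335 (50%) | 28.2% | 33.0% |

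The shift that takes 5% to 10% is 0.158 points (25 per group) or 0.144 points (30 per group). The values of d are assumptions. The table shows how sensitive the test is to a shift from any source; it is not evidence that the instruction causes one.

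**The case against.** The strongest reply is that the trial compares regimens. Section 6.3 defines each arm as brush plus instructions plus toothpaste, and 8.3 says openly that the instructions depend on the arm. This stands in part: instructions belong to each arm, and technique must follow the device. But 6.3 lists the same kinds of instruction for both arms and does not reserve pressure coaching for the test arm, while 4.1 and 5.1.1 attribute the comparison to the toothbrush.

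A second reply is that controls may get pressure advice from sources not reproduced. This stands as a limit. A reader might infer that control patients receive no pressure advice at all; the documents do not support that.

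A third is that the sensor already encourages a lighter touch, so the spoken sentence may add little. That is possible, and nothing in the documents says how much it adds. Likewise, force is named as a risk factor for recession, one item of five, in a section that calls the cause of recession unclear.

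A reader might also see a conflict between 8.3 and the appended sonic-brush manual, which speaks of "pressing firmly to make the bristles reach the gumline or slightly beneath the gumline". That reading does not hold up. The phrase belongs to placing the bristles before the brush is switched on, and the brushing step that follows asks the user to hold them gently and not to scrub. Section 8.1 also says: "The test sites will be treated with the investigational device following the instructions of this protocol".

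On intensity, low is the first-use default and the mode is fixed, so only one setting is open. That makes the gap small but does not close it.

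**Conclusion.** The point holds in a limited form. Section 8.3 scripts light pressure for one arm and no pressure level for the other, in a trial whose primary endpoint is abrasion. This leaves an avoidable alternative explanation for a favourable test-arm result.

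The size of any effect is unknown and cannot be derived from the documents. A reader might take the rejection rates above as a measure of inflated type I error in this trial. They are not: they apply to any assumed shift of that size. The figures that rest on the plan alone are the significance thresholds of 0.48 points (25 per group) and 0.43 points (30 per group), assuming an SD of 0.84 in both arms and a t-test.

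The open intensity setting limits how the test-arm result can be described. It is not a demonstrated bias. The change is worth making before enrolment because it costs almost nothing. Confidence is medium, because part of what control patients are told is not visible.

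**What to change.** - In 8.3, move the light-pressure sentence into the shared text above the two arm-specific paragraphs. Leave the movement technique device-specific.
- Name one intensity setting for the sonic brush, for both supervised and home brushing, ideally the one used in the preliminary study. State that the pressure sensor stays on.
- Add the intensity actually used to the existing Day 90 patient-reported usage item.
- If the sponsor wants light-pressure coaching to be part of the test regimen only, say so in 5.1.1 and attribute the result to brush plus instruction.

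The cost is a few sentences in the protocol and one extra answer at Day 90. Test patients have slightly less freedom in how they use the device. Sample size, visits and analysis do not change.
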